Families will be recruited from pediatric practices in our Practice-based Research Networks (PBRNs) in several ways. Each practice will have children who meet age, height, and weight criteria flagged in their charts, and we will use multiple approaches to recruit families. First, we will establish a ResearchMatch approach to recruiting in each PBRN. ResearchMatch, an online recruitment tool, will accrue families in one of two ways. At intake for a well- or sick-child visit, forms designed to acquaint families with the study will be introduced by PLAN coaches, and families can sign up for additional information about this study. Their information will be entered into a database by the PLAN coaches, and they will be contacted if they meet criteria. In addition, we will set up a website that they will be directed to in a flyer, and they can sign up to participate from the website. Since the pediatrician generally will not have information on parental health, this will need to be collected prior to deciding study eligibility, and the family database will assist in this endeavor by including information about all family members after a phone screen is conducted by the PLAN coaches with the participating parent. Second, PBRN practices post study advertisement at offices for interested families to visit the study website to complete questionnaires to ensure they meet eligibility criteria. If the families meet eligibility criteria, a PLAN coach will follow up with the families to schedule their first appointment at their earliest convenience. At this appointment, the PLAN coach will confirm the families' interest to participate and eligibility prior to participation. Third, Plan coaches will meet with families during well-child visits to introduce the study, assess their interest, and explain next steps. Each of these methods in collecting their information regarding interest and eligibility will be preceded by getting their verbal consent over the phone or a check box indicated on the web pages.

During recruitment, PLAN coaches will explain that there is a 50/50 possibility of getting one treatment over the other treatment. This will be like a flip of the coin and no one can just pick one treatment or the other. This study is testing if the FBT is as good as the care provided by their doctors normally given or better. Randomization will occur after the first appointment.

Inclusion Criteria

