Power computations for PLAN employ simulations and two-sided tests at the 0.05 level of significance. The simulations reflect the planned primary analysis of covariance and the fact that this is an individually randomized group treatment trial with the coach (N=3 per site) nested within the site (N=4 sites) in the FBT group but with no such nesting in the UC group. The analysis of covariance that is simulated in the power computations treats the 24-month value of the outcome measure as the dependent variable and the baseline value as a covariate. The use of this approach reflects the primary study goal of comparing 24-month values across groups, with the outcome being compared being percent over normalized BMI in the participating child. Each result is based on 1000 simulations.

Tabulated power values employ sample sizes of 528 and that are between 65% and 95% of that total. Effect size estimates are generated using considerations and preliminary data discussed below. Usual care data involving an intervention and subjects most similar to our UC group is provided by Kalarchian⁶¹ who randomized 81 8-12-year-old children with obesity to a usual care control condition and found an average percent overweight change of -0.17 ± 10.08 at 1 year. We expect some deterioration in this group at 2 years but will assume conservatively for the purpose of power computations that the two-year change will be 0 ± 10.08 in the UC group in the proposed research. Our estimated change in the FBT group begins with a review of seven studies^{20,62-67} authored by [name]. There were 314 overweight/obese children in those studies who received FBT interventions similar to the one we will employ. When we combined

the data for those 314 children, we found an overall average decrease in percent over BMI of 10.6 ± 15.3 at 24 months.

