In translating the above decrease of 10.6 ± 15.3 in percent over BMI at 24 months into the setting of the proposed research, we emphasize that the seven referenced studies implemented FBT in controlled academic settings where we anticipate better performance than is likely in the family practices we will employ in this study. To estimate the degree to which the effect is likely to be attenuated when we switch from highly controlled to more “real life” settings, we considered the following. The child weight management intervention MEND (Mind, Exercise, Nutrition, Do it) focused on children age 7-13 who exceeded the 91st weight percentile. MEND employed both (1) a community-based mass-implementation intervention⁶⁸ involving many programs and 9563 subjects who provided complete data and (2) a rigorous randomized trial⁶⁹ (N=116) analogous to the seven [name] studies referenced in the preceding paragraph. The 12-month results were reductions in BMI of 0.79 kg/m^2 in the community study as compared to 1.04 kg/m^2 in the intervention arm of the randomized trial. Thus, the reduction in the community-based MEND intervention was 76.0% of the magnitude that was observed in the family-based arm of the randomized trial.

Based on this 76.0%, our computations conservatively assume changes in the intervention group that are 50%, 60%, and 70% of the previously observed change of 10.6 ± 15.3 that was observed in the rigorous academic environment of [name] studies.^{20,62-67} Thus, we base our power on a comparison of projected reductions of 5.3 ± 15.3 (50% of 10.6 ± 15.3), 6.4 ± 15.3 (60% of 10.6), and 7.4 ± 15.3 (70% of 10.6) in the FBT group as compared to 0 ± 10.08 in the UC group. In addition, given projected standard deviations of 15.3 and 10.08 in the two groups, we use the maximum and the mean of those two values and thereby compute power assuming standard deviations of both 15.3 and 12.7. In performing the calculations summarized below, we emphasize that we will have actual or imputed 24-month data on all subjects. To see details of how we will impute the 24 month values when necessary, please see the section below titled “Implementation of the Intention-to-Treat Principle.”

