Table 1 contains the results of the power computations using the parameters discussed above, assuming the compound symmetry covariance structure in both study arms and assuming an intraclass correlation coefficient (ICC) in the UC group of 0.01 and ICCs in the FBT group of 0.04, 0.06, 0.10, and 0.15. We assume a small ICC in the UC group of 0.01 because there is no clustering within that group meaning that the ICC should be essentially zero. While we do not have data with which to estimate the ICC in the FBT group, we note that many cluster trials that involve group interventions have reported ICCs in the 0.01 to 0.05 range. Since the PLAN intervention is individualized and since we expect PLAN children to have no contact with one another, we do not face the impact on the ICC that is present in many cluster trials. This argues for a very small ICC in the FBT group. By contrast, the fact that the same coach will be responsible for multiple children will inevitably increase the ICC above where it might otherwise be. Based on these considerations, we tabulate power for ICCs in the FBT group that range from 0.04 to 0.15. However, the many other studies that have used group interventions while yielding ICCs below 0.05 suggests that the ICC ultimately observed in PLAN will be substantially less than 0.1.

Results in Table 1 indicate that if we recruit 100% of our original target of 528 families, power will be excellent for all tabulated scenarios with an ICC in the FBT group of 0.1 or less. For an ICC

no bigger than 0.1, power remains adequate for most scenarios if we recruit at least 80% of the target (N = 432). If recruitment is below the 80% figure, an adequate power of at least 0.8 requires either the smaller of the two tabulated standard deviations or a mean difference that is at least 60% of the value observed in [name] studies (difference at least 6.4).

Table 1: Statistical power for two sided tests at the 0.05 level of significance.

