Computations are for the primary outcome which is the percent over the 50th percentile of BMI in children. Results are generated using 1000 simulations of the primary analytic model: an analysis of covariance with the 24-month value as the dependent variable and the baseline value as a covariate. The analysis reflects the fact that this is an individually randomized group treatment trial in which the coach is nested within the site within the FBT group but which is different from a classic cluster randomized trial in that there is no such nesting within the control (UC) group. The total number of randomized families is assumed to range from 65% to 100% of the target of 528. Tabulations assume an ICC of 0.01 in the UC group and of 0.04, 0.06, 0.10, and 0.15 in the FBT group, mean differences of 5.3, 6.4 and 7.4 (which represent 50%, 60%, and 70% of observed results in previous studies), and standard deviations of 12.7 and 15.3.

(N's Adjusted Below, DSMB approved protocol addenda, 9.29.19).

ICC		SD	Mean diff	Statistical power associated with sample sizes ranging from 65% to 100% of original target of 528							
FBT grp	UC grp			N=528 (100%)	N=502 (95%)	N=476 (90%)	N=449 (85%)	N=422 (80%)	N=396 (75%)	N=370 (70%)	N=344 (65%)
0.04	0.01	12.7	5.3	0.95	0.95	0.94	0.92	0.93	0.92	0.89	0.89
			6.4	0.99	0.98	0.99	0.98	0.99	0.98	0.98	0.97
			7.4	1.00	1.00	1.00	1.00	1.00	1.00	0.99	1.00
		15.3	5.3	0.84	0.83	0.83	0.81	0.80	0.76	0.76	0.74
			6.4	0.96	0.94	0.95	0.92	0.91	0.91	0.88	0.87
			7.4	0.99	0.99	0.99	0.98	0.97	0.97	0.97	0.96
0.06	0.01	12.7	5.3	0.92	0.91	0.90	0.90	0.88	0.87	0.85	0.84
			6.4	0.98	0.98	0.98	0.98	0.97	0.96	0.95	0.95
			7.4	1.00	1.00	1.00	1.00	0.99	0.99	0.99	0.99
		15.3	5.3	0.80	0.79	0.77	0.78	0.74	0.73	0.70	0.68
			6.4	0.92	0.91	0.92	0.91	0.88	0.87	0.85	0.84
			7.4	0.97	0.97	0.96	0.97	0.96	0.95	0.93	0.94
0.10	0.01	12.7	5.3	0.85	0.83	0.81	0.83	0.80	0.80	0.76	0.76
			6.4	0.95	0.94	0.94	0.93	0.91	0.92	0.91	0.88
			7.4	0.98	0.98	0.98	0.98	0.98	0.97	0.97	0.97
		15.3	5.3	0.69	0.68	0.69	0.63	0.67	0.65	0.62	0.60
			6.4	0.84	0.82	0.84	0.81	0.81	0.77	0.76	0.78
			7.4	0.94	0.94	0.92	0.92	0.91	0.89	0.89	0.87
0.15	0.01	12.7	5.3	0.73	0.75	0.71	0.72	0.69	0.70	0.70	0.68
			6.4	0.86	0.85	0.83	0.85	0.85	0.84	0.83	0.81
		7.4	0.95	0.95	0.95	0.94	0.94	0.93	0.93	0.92	
			5.3	0.57	0.59	0.55	0.56	0.53	0.53	0.52	0.52

[figure not shown]
		15. 3	6.4 7.4	0.73 0.86	0.74 0.82	0.70 0.86	0.73 0.83	0.71 0.82	0.67 0.81	0.68 0.80	0.65 0.79

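### The power table gives both arms one SD, so no row shows the plan's own case (15.3 in FBT, 10.08 in UC); the 12.7 rows overstate power for that case and the 15.3 rows understate it

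*Combined protocol and SAP*

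**What the plan says.** All of this is in Statistical Considerations, Primary Analysis, section 1 (Sample Size and Statistical Power) of the combined protocol and SAP.

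- For usual care the plan assumes "the two-year change will be 0 ± 10.08 in the UC group in the proposed research". For FBT it projects reductions of 5.3, 6.4 or 7.4, each with SD 15.3.
- It then collapses the two SDs: "we use the maximum and the mean of those two values and thereby compute power assuming standard deviations of both 15.3 and 12.7". Table 1 has one SD column and no row pairing 15.3 with 10.08.
- The simulations are described as having "the coach (N=3 per site) nested within the site (N=4 sites) in the FBT group" and no such nesting in UC. FBT ICCs run from 0.04 to 0.15. The UC ICC is set at 0.01, with the remark that it should be essentially zero.
- Tests are "two-sided tests at the 0.05 level of significance", with 1000 simulations per cell. On size: "The total number of randomized families is assumed to range from 65% to 100% of the target of 528".
- The text calls power at 528 families excellent in every tabulated scenario with FBT ICC up to 0.1. For ICCs up to 0.1 it adds that "power remains adequate for most scenarios if we recruit at least 80% of the target". Below that level, "an adequate power of at least 0.8 requires either the smaller of the two tabulated standard deviations" or a difference of at least 6.4.

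**The concern.** With equal arms and no clustering, replacing two SDs by their mean would do little harm: 12.7 against a root mean square of 12.96. Here the design effect multiplies only the FBT variance, and FBT has the larger SD. Averaging moves variance out of the arm where it is inflated about threefold (at ICC 0.10) and into the arm where it is hardly inflated. The standard error comes out too small in the 12.7 rows and too large in the 15.3 rows.

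What is at stake is the reading of the table, not the analysis. The conclusions about power at full recruitment, and about what remains if recruitment falls short, draw partly on the 12.7 rows. The protocol's halting rules also call for conditional power if recruitment or retention underperforms, so the planning inputs may be used again.

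**Working it through.** **Inputs.** Two-sided 0.05. N = 528; recruitment material describes allocation thus: "there is a 50/50 possibility of getting one treatment over the other treatment", so n = 264 per arm. There are 12 coaches (3 at each of 4 sites), so m = 264/12 = 22 families per coach. SDs and differences are as above.

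**Formula.** Var = SD_F²[1+(m−1)ICC_F]/n + SD_U²[1+(m−1)ICC_U]/n, with power from the noncentral t.

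**Step 1: reproduce the printed table.** Take SD 12.7 in both arms, ICC_F 0.10 and ICC_U 0.01. FBT: 161.29 × 3.1 = 500.0. UC: 161.29 × 1.21 = 195.2. Var = 695.2/264 = 2.633 and SE = 1.623. With 11 df, power at difference 5.3 is 0.844; the table prints 0.85. This variant comes within 2 points of 79% of the 192 cells. A variant with UC unclustered and 9 df reaches 85%. A plain normal approximation reaches only 28%. A common SD with small degrees of freedom therefore describes the table well.

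**Step 2: use the plan's SDs.** Take 15.3 in FBT, 10.08 in UC, and UC unclustered. FBT: 234.09 × 3.1 = 725.7. UC: 101.6. Var = 827.3/264 = 3.134 and SE = 1.770. The like-for-like value with 12.7 in both arms and UC unclustered is (500.0 + 161.3)/264 = 2.505, SE 1.583. The SE ratio is 1.12, so the single SD that would match is about 14.2 (13.7, 13.9, 14.2 and 14.4 at ICC 0.04, 0.06, 0.10 and 0.15).

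Power at N = 528, difference 5.3:

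| FBT ICC | SD 12.7 printed | SD 12.7 recomputed | SD 15.3 printed | SD 15.3 recomputed | 15.3/10.08, 11 df | 15.3/10.08, Satterthwaite df |
|---|---|---|---|---|---|---|
| 0.04 | 0.95 | 0.941 | 0.84 | 0.834 | 0.924 | 0.940 |
| 0.06 | 0.92 | 0.911 | 0.80 | 0.785 | 0.877 | 0.895 |
| 0.10 | 0.85 | 0.844 | 0.69 | 0.695 | 0.778 | 0.796 |
| 0.15 | 0.73 | 0.760 | 0.57 | 0.601 | 0.668 | 0.684 |

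The recomputed single-SD columns use ICC_U 0.01 and 11 df; the last two columns have UC unclustered. Keeping ICC_U at 0.01 lowers the last two columns by about 1 point (for example 0.768 and 0.789 at ICC 0.10).

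**Step 3: size of the overstatement, like for like** (12.7 in both arms minus 15.3/10.08; UC unclustered on both sides, 11 df, N = 528), in points:

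| Difference | ICC 0.04 | 0.06 | 0.10 | 0.15 |
|---|---|---|---|---|
| 5.3 | 3.1 | 5.0 | 8.3 | 10.8 |
| 6.4 | 0.9 | 2.0 | 4.9 | 8.3 |
| 7.4 | 0.2 | 0.6 | 2.2 | 5.1 |

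Over the variants that reproduce the table, the ranges are about 3 to 11, 1 to 9, and under 1 to 6 points.

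**Step 4: reduced recruitment, ICC 0.10, difference 5.3.** At N = 422, m = 17.58 and the design effect is 2.658. Var = (622.3 + 101.6)/211 = 3.431, SE = 1.852, and power is 0.74 (11 df) or 0.76 (Satterthwaite). At N = 396, m = 16.5 and the design effect is 2.55. Var = (596.9 + 101.6)/198 = 3.528, SE = 1.878, and power is 0.73 or 0.75. With ICC_U 0.01 the ranges extend down to 0.73 and 0.72. Both cells print 0.80.

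**The case against.** The choice is disclosed. Both arm SDs are stated, and every 12.7 row has a 15.3 row beside it that errs on the safe side. The projected case lies between them: at ICC 0.10 and difference 5.3, 0.69 < 0.78 < 0.85. The plan also expects an ICC well below 0.1. All of that stands, and it makes this a gap in what is tabulated, not a hidden error.

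The claim about 80% recruitment also survives. With the plan's SDs at N = 422, eight of the nine combinations of ICC (up to 0.10) and difference give about 0.83 or more; only ICC 0.10 with 5.3 falls short.

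The sentence about recruitment below 80% can be read as stating only a necessary condition, and Table 1 itself prints 0.76 for SD 12.7, ICC 0.10, difference 5.3 at N = 370. That is fair. But a reader will still take the smaller SD as one of two ways to reach 0.8, and 12.7 in both arms is not a case that the plan projects.

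Printed cells carry simulation error of about 1.4 to 3 points. The ICC 0.15 cell (0.73) lies below its own N = 502 neighbour (0.75), so printed-minus-recomputed differences are partly noise. The sizes above therefore compare calculated with calculated values.

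**Conclusion.** The point holds as a matter of presentation and interpretation. No row shows the comparison on which the plan says power is based, and the 12.7 rows are too favourable to it by amounts that depend strongly on the difference and the ICC. At difference 5.3 and ICC 0.10, power is about 0.77 to 0.80 at N = 528 (0.85 printed), 0.73 to 0.76 at N = 422 (0.80 printed) and 0.72 to 0.75 at N = 396 (0.80 printed). Calling power excellent there is not supported; the printed 0.69 in the matching 15.3 row already does not fit that word.

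A reader might infer that the trial is underpowered, or that Table 1 was computed wrongly. The documents support neither. At ICC 0.04 to 0.06, power with the plan's SDs is about 0.87 to 0.94 at N = 528 even for the smallest difference, and the printed cells largely reproduce under a common SD. A reader might also infer that all 12.7 rows are off by a similar amount; at difference 7.4 and low ICC the gap is under 1 point.

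Assumptions: equal coach caseloads, although some sites have backup and floating coaches; SDs of change used as residual SDs, with no ANCOVA gain modelled because no baseline-to-24-month correlation is given; and one SD in both arms, inferred from the single SD column and from the fit.

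**What to change.** Re-run the existing simulation with SD 15.3 in FBT and 10.08 in UC and coach clustering in FBT only, and add these rows to Table 1 beside the present ones. State the assumed baseline correlation, if one was used.

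Then restate the text above the table. At ICC 0.10 and difference 5.3, power at 528 families should not be described as excellent. Below 80% recruitment, the smaller tabulated SD should not be offered as a route to 0.8. The statement that power is adequate for most scenarios at 80% can stay.

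The cost is one simulation re-run and a few sentences, and some stated power figures become less favourable. Sample size and primary analysis are unchanged.
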